5.0 Methods

5.1 Measures

The following outcome, safety, and process measures will be used in the study. This study will utilize methods described in the Treatment Manual for conducting MDMA-assisted Psychotherapy combined with methods from the CBCT for PTSD manual. The integration of these manuals will provide the researcher with a consistent psychotherapy approach and test an investigational form of drug-assisted psychotherapy. The Treatment Manual is not intended to define all interactions that occur in the therapy. All psychotherapy sessions, including Experimental Sessions, may be recorded to audio and video, with all recordings preserved for research and training purposes.

Page 32 of 89

Table 4: Study Measures

Measure	Purpose	Administration	Time/ # of items	When	PTSD+ Participant	CSO Participant
Screening, Inclusion & Exclusion						
SCID for DSM-5- AXIS 1 only and then screening question for AXIS 2 modules (do modules if needed)	Screening	Interview	60 minutes	Baseline	Y	Y
Primary & Secondary Outcomes						
CAPS-5 Clinician Administered PTSD Scale for DSM-5	PTSD Severity	Interview	90 minutes	Baseline, Endpoint, LTFU 3, 6	Y	N
PCL (last month) PTSD Checklist for DSM-5	PTSD symptoms	Self-report	10-15 minutes	Baseline (with LEC), Endpoint, LTFU 3, 6	Y	Y (PCL- Participant)
PCL (since last visit) PTSD Checklist for DSM-5	PTSD symptoms	Self-report	10-15 minutes	Integrative Sessions, Midpoint	Y	Y (PCL- Participant)
PCL (since last week) PTSD Checklist for DSM-5	PTSD symptoms	Self-report	10-15 minutes	Visit 2	Y	Y (PCL- Participant)
BDI-II Beck Depression Inventory	Depression Symptoms	Self-report	5-10 minutes	Baseline, Midpoint, Endpoint, LTFU 3, 6	Y	Y
ERQ Emotional Regulation Questionnaire	Emotion regulation	Self-report	4-6 minutes	Baseline, Midpoint, Endpoint, LTFU 3, 6	Y	Y
IRI Interpersonal Reactivity Index	Compassion empathy, social functioning	Self-report	10 minutes	Baseline, Day after Experimental Sessions, Midpoint, Endpoint, LTFU 3, 6	Y	Y
PSQI Pittsburg Sleep Quality Index	Sleep Quality	Self-report	5-10 minutes	Baseline, Midpoint, Endpoint, LTFU 3, 6	Y	Y
PTGI Post Traumatic Growth Inventory	Growth after Trauma	Self-report	5-10 minutes	Baseline, Midpoint, Endpoint, LTFU 3, 6	Y	Modified for participant. Participant will rate the PTSD participant. Y
TAS-20 Toronto Alexithymia Scale	Emotion recognition, alexithymia	Self-report	5 minutes	Baseline, Midpoint, Endpoint, LTFU 3, 6	Y	Y

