5.1.1 Outcome Measures

The primary measure will be change in CAPS scores from Baseline to Primary Endpoint. A qualified, blinded IR will perform the CAPS at Baseline and outcome measurement time points. The IR will not be present during the participant's Experimental Sessions nor have any information regarding the Experimental Sessions. CAPS-5 [136] is a semi-structured clinical interview used to assess index history of DSM-5-defined traumatic event exposure [36], including the most distressing event, time since exposure, and total number of exposures, as well as frequency and severity of posttraumatic stress symptoms, as evidenced by CAPS total score. The CAPS provides diagnostic status (presence versus absence) of PTSD as well as PTSD symptom severity. Changes in the CAPS total score will be used as the primary PTSD outcome measure, and will be the primary determinant of effect size for this pilot study. All assessments, including those at Baseline, will use the CAPS assessment of symptoms over the last month. The IR will administer the CAPS at visits described in Table 3: Time and Events either in person or via telemedicine. Studies for validation of this measure are ongoing.

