The secondary measure of PTSD symptoms will be the PCL (reported for last month, since last visit, and since last week per Table 4), a self-report measure designed to follow DSM-5 criteria for assessing PTSD. The PTSD Checklist (PCL-5) [137] is a 20-item selfreport questionnaire in which respondents indicate the presence and severity of PTSD symptoms, derived from the DSM-5 symptoms of PTSD [36]. Participants indicate how much distress they have experienced due to symptoms such as "Repeated, disturbing memories, thoughts, or images of a stressful experience from the past," "Trouble remembering important parts of a stressful experience from the past," and "Feeling irritable or having angry outbursts" on a five-point Likert-type scale (1 = not at all, 5 = extremely). The total PCL-5 score (a sum of all 20 items) provides an index of overall PTSD symptom severity. Reports on reliability and validation of the PCL-5 are underway; preliminary comparison with the PCL for DSM IV suggests that the cut-off for PCL-5 is 11 to 14 points lower than for the PCL [137]. Participants will complete the PCL-5 questionnaire, as specified in Table 3: Time and Events. The PTSD+ participant will complete it based on their own symptoms and the CSO participant will complete it based on the PTSD+ participant.

The BDI-II is a 1996 revision of the BDI, a 21-item self-report measure [138, 139] that will serve as a measure of depression according to DSM-IV criteria [140]. The BDI-II has been validated, has high internal consistency and good test/re-test reliability, and is not overly sensitive to daily variations in mood. It takes five to ten minutes to complete [140]. Score cutoffs indicate: 0-13 minimal depression, 14-19 mild depression, 20-28 moderate depression, and 29-63 severe depression. Initial and subsequent studies report that the BDI-II total score has a reliability coefficient of 0.90 to 0.91 and that it is related to other measures of depression symptoms [140, 141]. Higher scores indicate more severe depressive symptoms. Both the participants will complete the BDI-II according to Table 3: Time and Events.

The ERQ is a brief measure of self-reported emotion-regulation. It consists of ten items that is intended to assess means of coping with emotions via changing them, as through reappraisal, or suppressing them [142]. Respondents rate indicate the extent of their

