5.2.7 Evaluation and Preparation Visit at Midpoint (Visit 9 - Clinic Visit)

(Approximately 3 weeks after V3; prior to V10)

CBCT Manual Sessions 10 and 11

Sessions 10 and 11 – Making meaning of the trauma. Discussion of the themes of trust and control.

The midpoint evaluation will occur approximately 20 days after the first Experimental Session. Dyads who have withdrawn from treatment but have continued for follow-up will also complete this time point. This session will be recorded to audio/video.

- a. The therapists will assess suicidal ideation and behavior with the C-SSRS
- b. General Wellbeing will be assessed
- c. Collect AEs and medications, as described in Sections 8.0 and 9.0

The following self-report measures will be completed at the midpoint:

- PTGI (in reference to time since the trauma) for the PTSD+ participant and modified for the CSO participant to rate the PTSD+ participant
- PCL (since last visit) to assess PTSD symptoms for the PTSD+ participant and modified for the CSO participant to rate the PTSD+ participant
- TABS to assess trauma related beliefs for the PTSD+ participant and modified for the CSO participant to rate the PTSD+ participant
- MDI to assess dissociative symptomology for the PTSD+ participant and CSO participant
- SORTS to assess partner accommodation for the CSO participant
- BDI-II to assess depression symptoms for both the PTSD+ participant and CSO participant
- PSQI to assess sleep quality for both the PTSD+ participant and CSO participant.
 PSQI PTSD addendum will be completed by PTSD+ participant only
- ERQ to assess emotional regulation for both the PTSD+ participant and CSO participant
- TAS-20 to assess emotion recognition, alexithymia for both the PTSD+ participant and CSO participant
- QRI to assess relationship satisfaction for both the PTSD+ participant and CSO participant
- CTS to assess conflict, tactics and aggression for both the PTSD+ participant and CSO participant
- IPF to assess psychosocial functioning for both the PTSD+ participant and CSO participant
- MSIS to assess social intimacy for both the PTSD+ participant and CSO participant
- IRI to assess compassion, empathy and social functioning for both the PTSD+ participant and CSO participant

- IPC for both the PTSD+ participant and CSO participant
- CSI for both the PTSD+ participant and CSO participant, if in a romantic relationship

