# 4. Additional Exploratory Analysis

Pearson Correlations will be computed between PTSD+ participants' CAPS-5 scores and CSO participants' outcomes (all) [4]. This analysis will be conducted for baseline, midpoint (visit 9), primary endpoint (visit 16), 3-month follow-up (visit 17), and primary endpoint (visit 18). Correlations (*r*) and *p* values will be reported to assess the direction and magnitude of these relationships. This analysis is intended to explore the potential impact of CSO participants' responses to the given treatment on PTSD+ participants' CAPS-5 scores over time.

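### Same-visit correlations of CAPS-5 with CSO scores cannot show how CSO response to treatment relates to CAPS-5, and no CAPS-5 is scheduled at visit 9

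*SAP*

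**What the plan says.** The SAP's fourth efficacy section states that "Pearson Correlations will be computed between PTSD+ participants' CAPS-5 scores and CSO participants' outcomes (all"), and lists the visits: "This analysis will be conducted for baseline, midpoint (visit 9), primary endpoint (visit 16), 3-month follow-up (visit 17), and primary endpoint (visit 18"). Coefficients and p values are to be reported. The stated purpose is to "explore the potential impact of CSO participants' responses to the given treatment on PTSD+ participants' CAPS-5 scores over time". The section defines no change score, lag or baseline adjustment.

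The CAPS-5 schedule is narrower than that list of visits. Protocol Table 4 places the CAPS-5 at "Baseline, Endpoint, LTFU 3, 6". Protocol section 5.1.1 ties administration to the schedule: "The IR will administer the CAPS at visits described in Table 3: Time and Events". The CAPS row of Table 3, in the protocol and in the SAP's own copy, is ticked only at screening and at visits 16, 17 and 18. Protocol section 5.2.7 introduces the visit 9 scales with "The following self-report measures will be completed at the midpoint", and neither that list nor the clinician items before it includes a CAPS interview.

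Some CSO outcomes are ratings of the other dyad member. Of the PCL-5, protocol section 5.1.1 says "the CSO participant will complete it based on the PTSD+ participant". Protocol section 5.2.1 treats the CSO versions of the PTGI and TABS in the same way.

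**The concern.** Response to treatment, followed over time, means change. A correlation of scores at one visit combines two things: stable differences between dyads that were there at screening, and any link between the two members' changes. Only the second bears on the stated question. The baseline set, taken before any treatment, holds none of it. The midpoint set lacks one of its two variables.

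A post-treatment coefficient could therefore be read as evidence about CSO response when it reflects only how distressed dyads differed from less distressed ones at entry. A real link between responses could also be diluted or cancelled. The CSO ratings of the PTSD+ participant add a further risk: their correlation with CAPS-5 may be mere agreement between two raters about the same person.

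**Working it through.** **The plan's own figure.** The documents give no design figure for this analysis. The protocol's one computed figure, 62% power for the paired t-test (effect size 0.8, n = 10, two-sided 0.05), reproduces at 61.6% from the noncentral t distribution. It is not affected by this point.

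**Levels against change.** Standardise both baseline scores to SD 1. Let each later score be baseline plus a change with SD s, uncorrelated with baseline within and across the two members. Let c0 be the correlation of the two baselines and rc the correlation of the two changes. Then:

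- variance of each later score = 1 + s²
- covariance of the two later scores = c0 + rc·s²
- correlation at the later visit = (c0 + rc·s²) / (1 + s²)

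The documents supply none of c0, rc or s, so these values are assumptions:

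| c0 | rc | s | correlation at the later visit |
|---|---|---|---|
| 0.6 | 0 | 1 | 0.6 / 2 = 0.30 |
| 0 | 0.6 | 1 | 0.6 / 2 = 0.30 |
| 0.5 | 0 | 0.5 to 1.5 | 0.40 to 0.15 |
| 0 | 0.5 | 0.5 to 1.5 | 0.10 to 0.35 |
| 0.5 | −0.5 | 1 | 0 |

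The first two rows are opposite situations with the same result. In the last row, baselines and changes are both associated and the level correlation is zero.

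**Visit 9.** No dyad has a scheduled CAPS-5 there, so four of the five listed visits are computable.

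**Number of tests.** SAP section 5.1 lists 17 outcome measures. Removing CAPS-5 leaves 16 for the CSO, counting one score per instrument.

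- Computable as planned: 16 × 4 = 64 tests; 64 × 0.05 = 3.2 expected false positives under the null.
- Change correlations at visits 16, 17 and 18: 16 × 3 = 48 tests; 48 × 0.05 = 2.4.

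**Precision.** The critical |r| is t / √(t² + df), with two-sided alpha 0.05.

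- 10 pairs, no covariate, 8 df: 2.306 / √(5.318 + 8) = 0.63
- one covariate, 7 df: 2.365 / √(5.592 + 7) = 0.67
- two covariates, 6 df: 2.447 / √(5.988 + 6) = 0.71

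For an observed r of 0.5 with 10 pairs, the Fisher interval is tanh(0.549 ± 1.96/√7), or −0.19 to 0.86.

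**The case against.** The analysis is labelled exploratory, the trial is a 10-dyad pilot not meant to lead to registration, and the primary test does not depend on it. The visit 9 entry would produce an empty set rather than a wrong answer. SAP section 4.0 makes the protocol the definitive reference, and visit 18 is correctly named in the SAP's section on long-term follow-up. All of that stands, and it limits the consequence. It does not make a level correlation answer a question about response.

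Baseline is listed as a time point of its own and can serve as a reference for the later ones. That is also fair. A reader might infer that a baseline association will be reported as an effect of response, but nothing in the SAP says so.

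Four other stronger readings are not supported:

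- **80 tests and four false positives.** This multiplies 16 measures by all five listed visits, but 16 of those tests have no CAPS-5 input. The supportable figures are 64 and 3.2.
- **Time order from CSO change to visit 9 against CAPS-5 change to visit 16.** With no CAPS-5 at visit 9, the CAPS-5 change runs from baseline and covers the same early period, so precedence cannot be shown. Adding this set would also bring the change correlations back to 48 + 16 = 64.
- **The r = 0.30 example as an estimate for this trial.** It is algebra under assumed values. It shows that the quantity is not identified and says nothing of what will be observed.
- **A CAPS-5 value at visit 9 through early termination.** The SAP maps termination data to a nearby scheduled visit, so an isolated value from a dyad that stops could be labelled visit 9. That cannot supply the planned midpoint set.

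**Conclusion.** The point holds as a mismatch between an exploratory analysis and its stated purpose. Same-visit correlations at visits 16, 17 and 18 do not identify an association between CSO response and CAPS-5 response, the baseline set contains no response, and the visit 9 set cannot be formed as planned. The failure of identification does not depend on the particular numbers. The value 0.30 does: it assumes change independent of baseline and equal SDs.

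The counts of 64 tests and 3.2 expected false positives assume one score per instrument. They would rise if subscales of the ERQ, IRI, TABS or IPC were tested separately. The critical |r| of 0.63 assumes 10 complete pairs; the CSI is for romantic couples only and may have fewer.

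A reader might take this as a threat to the trial's main result. It is not: the paired t-test of CAPS-5 from baseline to visit 16 uses none of these correlations. The visit 18 label is clerical.

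**What to change.** In the SAP's section on additional exploratory analysis:

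1. Delete visit 9 from the CAPS-5 correlations and relabel visit 18 as the 6-month follow-up.
2. At visits 16, 17 and 18, replace the level correlations with correlations between CSO change from baseline and CAPS-5 change from baseline, adjusted for baseline scores. Name in advance which baseline scores are used.
3. Keep the baseline correlation only as a descriptive reference.
4. Report r with 95% intervals, and describe the result as association, not impact. Make no claim of time order.
5. Report the CSO-completed PCL-5, PTGI and TABS separately, since they rate the PTSD+ participant.
6. Use PTGI change only if the recall frame is the same at both visits. Protocol section 5.1.1 moves the frame to the start of participation after baseline, while sections 5.2.7 to 5.2.9 keep it at time since the trauma.

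The cost is SAP wording. All the data are already scheduled. The number of tests falls from 64 to 48, with the baseline set as description only. The price is one or two degrees of freedom per correlation, which raises the critical |r| from 0.63 to about 0.67 with one covariate or 0.71 with two.

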#### 5. Process Measures

## Long-term Follow-up Questionnaire (LTFU Questionnaire)

The LTFU Questionnaire nominal variables will be described in terms of frequencies and percentages, while ordinal and non-normal continuous variables will be described using sample mean, standard deviations, and range. Results will be reported for the total sample and by PTSD+ participants and CSO participants.

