5.1.3 Process Measures

All psychotherapy sessions, including Experimental Sessions, may be recorded to audio and video, with all recordings preserved for research and training purposes.

The Reactions to Research Participation Questionnaire (RRPQ) [179] is an assessment of causes for taking part in research and responses to the experience of being a research participant. The RRPQ is intended to assess the participants' experiences as research participants, perceived reasons for consenting to be a research participant and perceived

freedom to take part in the study. This will be completed by the PTSD+ participant and the CSO participant according to Table 3: Time and Events.

The Long-term Follow-up Questionnaire has been developed internally by the sponsor to assess long-term benefits and harms of MDMA-assisted psychotherapy at the Long-term Follow-up Visits. Both the PTSD+ participant and the CSO participant will complete the Long-term Follow-up Questionnaire according to Table 3: Time and Events. The CSO participant will complete a modified version.

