## 6.0 Analyses

In general, nominal variables will be described in terms of frequencies and percentages and analyzed using chi square analysis. Ordinal and non-normal continuous variables will be described using sample median and range, and analyzed by non-parametric statistical tests, and approximately normal variables will be described using sample mean and standard deviations and analyzed by parametric statistical tests. All statistical tests will be two-sided and a difference resulting in a p-value of less than or equal to 0.05 will be considered statistically significant. All p-values will be rounded to and displayed in four decimals. P-value less than 0.0001 will be shown in tables as <0.0001. For any analysis that is called out as parametric, e.g. t-test, the parametric assumptions will be examined. If necessary, nonparametric analyses will be utilized, e.g. Wilcoxon rank-sum test.

Clinical data will be presented in tabular format. Data not subject to analysis according to this plan will not appear in any tables or graphs but will be included in the data listings. Analyses will be carried out with SAS Version 9.4 (or higher). Selected results may be presented graphically using standard graphical software.

Post-hoc exploratory analyses not identified in this SAP may be performed to further examine the study data. These analyses will be clearly identified as such in the final clinical study report.

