#### General Well-being

Therapists will assess PTSD+ participants' and CSO participants' general well-being using the General Well-being scale at each timepoint and on a daily basis for seven consecutive days after each experimental session. Frequencies, percentages, and mean (SD) total scores will be reported for the total sample and by PTSD+ participants' and CSO participants.

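### The SAP summarises ordinal Long-term Follow-up Questionnaire items by mean and SD, contrary to its own general rule, and adds a total-sample summary across two versions of the form; counts per response level, by role and visit, are needed

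*SAP*

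**What the plan says.** **General rule.** SAP 6.0 states: "Ordinal and non-normal continuous variables will be described using sample median and range". It keeps mean and standard deviation for approximately normal variables. The section opens by saying that the rule applies in general.

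**Rule for this questionnaire.** The SAP's entry under Process Measures begins: "The LTFU Questionnaire nominal variables will be described in terms of frequencies and percentages". It then says that "ordinal and non-normal continuous variables will be described using sample mean, standard deviations, and range". On grouping it says: "Results will be reported for the total sample and by PTSD+ participants and CSO participants". It does not say whether the two follow-up visits are summarised separately.

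**What the questionnaire is for.** Protocol 5.1.3 describes it as "developed internally by the sponsor to assess long-term benefits and harms of MDMA-assisted psychotherapy". Protocol Table 4 and section 5.2.9 give its purpose as process, outcome and safety. Table 3 schedules it at Visits 17 and 18 (3 and 6 months after Visit 15). Protocol 5.1.3 adds: "The CSO participant will complete a modified version". Table 4 and section 5.2.9 also say that the CSO's form is modified.

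**Where the SAP places it.** SAP 5.2 lists it as a process measure. It appears neither in SAP 5.3 (Safety Measures) nor under Safety Analyses.

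**A related wording point.** For General Well-being the SAP says: "Frequencies, percentages, and mean (SD) total scores will be reported for the total sample", and goes on to give the same by role. Protocol Table 4 lists this measure as a single clinician-rated item.

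**The concern.** The two SAP rules name the same classes of variable and prescribe different summaries, with no reason given for the departure. A programmer cannot follow both.

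The questionnaire is one of the places where a participant can report lasting benefit or harm, and its entry under Process Measures is the only measure-specific rule the SAP gives for it. With 10 dyads, one participant is 10% of a role. The natural question is how many people are at each level of a benefit or harm rating. Frequencies are promised for nominal items only, so an ordinal rating would be reduced to an average, a spread and two extremes.

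The total-sample column raises a second question. If an item is worded differently for the CSO, a mean over both roles averages answers to two different questions.

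**Working it through.** There is no stated figure to reproduce, because the plan attaches no number to this summary. The check compares the texts and then asks what the planned statistics can recover.

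**1. The texts side by side**

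| Variable class | SAP 6.0 | SAP, Long-term Follow-up Questionnaire |
|---|---|---|
| Nominal | frequencies and percentages | frequencies and percentages |
| Ordinal or non-normal continuous | median and range | mean, SD and range |
| Approximately normal | mean and SD | not mentioned |

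The conflict is confined to the second row.

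**2. Do mean, SD and range fix the number of people at the upper levels?**

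Assumption: an ordinal item scored 0 to 4. The documents give no item format. SD = √[(Σx² − n·mean²)/(n − 1)].

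*n = 10, one role*

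- Set A: one 0, six 2s, three 4s. Σx = 0 + 12 + 12 = 24. Σx² = 0 + 24 + 48 = 72.
- Set B: one 0, two 1s, six 3s, one 4. Σx = 0 + 2 + 18 + 4 = 24. Σx² = 0 + 2 + 54 + 16 = 72.
- Both sets: mean 24/10 = 2.4; SD = √[(72 − 57.6)/9] = √1.6 = 1.265; range 0–4.
- People scoring 3 or more: 3 in A, 7 in B.

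*n = 20, both roles together*

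- Set C: one 0, twelve 2s, seven 4s. Σx = 52, Σx² = 160.
- Set D: three 0s, sixteen 3s, one 4. Σx = 52, Σx² = 160.
- Both sets: mean 2.6; SD = √[(160 − 135.2)/19] = 1.142; range 0–4.
- People scoring 3 or more: 7 in C, 17 in D.

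So the planned summary does not determine the count.

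**3. Would the SAP's general rule do better?**

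- Set E (n = 10): five 0s, three 2s, one 3, one 4. Median (0 + 2)/2 = 1; range 0–4.
- Set F (n = 10): three 0s, five 1s, two 4s. Median 1; range 0–4.
- People scoring 1 or more: 5 in E, 7 in F.
- These sets also share the mean (13/10 = 1.3) and the SD (√[(37 − 16.9)/9] = 1.494).

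Median and range therefore do not give the count either. Aligning the questionnaire rule with SAP 6.0 removes the contradiction but does not supply the missing information. A table of counts per response level does.

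**4. The total-sample column**

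The SAP reports the total and each role. The PTSD+ summary is therefore available without the CSO data. What is open is the meaning of the total for any item that differs between the two forms, and the SAP does not restrict the total to common items.

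**The case against.** The other side has several good points.

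- **The general rule is only general.** A measure-specific section may depart from it. That is possible, but no reason is given, and reversing the summary for exactly the same classes looks like a drafting slip.
- **The number reporting long-term harm is not simply hidden.** A reader might infer that it is, but the documents do not support this. A yes/no harm item would be nominal and counted by role, and nothing shows which items, if any, are ordinal.
- **Pooling does not dilute the PTSD+ result.** A reader might infer this too, but the sentence that plans the total also plans both roles separately. The total is an additional column.
- **Mean and SD are not always the poorer choice.** Take one person at 4 and nine at 0, against four at 1 and six at 0. Both means are 0.4, but SD (1.26 against 0.52) and range (0–4 against 0–1) separate them, while the median is 0 in both. The departure from the general rule is therefore not what loses the counts.
- **Long-term harm is reported elsewhere.** The SAP tabulates adverse events and SAEs by subject incidence, reports events requiring medical attention by role through last follow-up, and gives C-SSRS positives by role and time period. This stands, with one limit: Table 3 ends collection of all AEs at Visit 16. At Visits 17 and 18 it continues SAEs, psychiatric or withdrawal AEs, and AEs requiring medical attention. A lasting effect outside those classes might appear mainly in the questionnaire.
- **General Well-being already has frequencies and percentages planned.** Correct. Only the notion of a total score for a one-item measure needs correcting.

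**Conclusion.** The point holds in a narrow form. The SAP contradicts its own general rule for ordinal and non-normal items of this questionnaire, and it plans a total across two versions of the form without limiting it to common items. For any ordinally scored benefit or harm item, the planned summary would leave the number of participants at each level undetermined: 3 or 7 of 10 in the illustration. That size rests on an assumed 0–4 item and on sets chosen to show how wide the ambiguity can be. It is not a forecast of the trial's data.

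The matter is minor. It concerns descriptive tables for a supplementary questionnaire and affects no test, the primary analysis or trial conduct. It is still worth correcting, because the protocol gives the instrument an outcome and safety purpose.

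**What to change.** In the SAP entry for the Long-term Follow-up Questionnaire:

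- For ordinal items, report number and percent at each response level, plus median and range.
- Present these by role, and separately at Visit 17 and Visit 18.
- Give a total-sample summary only for items worded identically in the PTSD+ and CSO forms.

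In the SAP entry for General Well-being, delete the reference to a total score, since the measure is one item. The frequencies and percentages planned there can stay as they are.

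The cost is a few words in the SAP and slightly longer tables. No new data are needed.
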